11.2.8 Pregnancy Reporting

All females of childbearing potential who participate in the study should be counseled on the need to practice adequate birth control and on the importance of avoiding pregnancy during study participation. Females should be instructed to contact the investigator or study staff immediately if pregnancy occurs or is suspected.

Male study participants will be instructed to practice birth control measures to prevent a partner's pregnancy during the subject's study participation and for 90 days following the last dose administration.

Pregnancy testing will be conducted prior to administration of study drug on every female of childbearing potential. A female who is found to be pregnant at the Screening Visit will be excluded from the study and considered to be a screening failure.

A female who becomes pregnant during study drug treatment will be immediately withdrawn from the study. Any female who becomes pregnant during treatment and within 30 days of discontinuing study drug will be followed by the investigator until birth or termination of pregnancy. Any pregnancy for which the estimated date of conception occurred prior to the Termination Visit of the study and for 30 days following study drug discontinuation, whichever is longer, must be reported.

If an adverse outcome of a pregnancy is suspected to be related to study drug exposure, this should be reported regardless of the length of time that has passed since the exposure to study treatment.

An induced abortion or a spontaneous abortion is considered to be a SAE and should be reported in the same timeframe and in the same manner as all other SAEs (see [Section 11.2.6.1](#)).

The investigator must report the pregnancy to [REDACTED] Pharmacovigilance using the Pregnancy Data Collection Form via the same fax number and/or email address as for SAE reporting. The investigator should contact the designated individuals who receive SAE notification and record information related to the pregnancy on an Exposure in Utero form provided by the sponsor or its designee.

Pregnancies must be reported as soon as possible, but no later than 1 business day, by Fax to:

[REDACTED]
[REDACTED]

Early Termination Visit assessments are required as soon as possible after learning of the pregnancy.

All Pregnancies must be followed to outcome. The outcome of the pregnancy must be reported as soon as possible but not later than one business day.

12. DATA SAFETY MONITORING BOARD

There will be no Data Safety Monitoring Board for this study.

13. STATISTICAL METHODS

13.1. Study Endpoints

13.1.1 Primary Efficacy Endpoint

The primary efficacy endpoint is the change in WOMAC LK3.1 OA pain score from Baseline and Week 4.

13.1.2 Secondary Efficacy Endpoints

Secondary efficacy endpoints include:

- WOMAC LK3.1 OA Index (pain) – change between Baseline and Week 1, and Week 2
- WOMAC LK3.1 OA Index (stiffness) between Baseline and Week 1, Week 2, and Week 4
- WOMAC LK3.1 OA Index (physical function) between Baseline and Week 1, Week 2, and Week 4
- WOMAC LK3.1 OA Index (composite score) between Baseline and Week 1, Week 2, and Week 4
- Patient Global Assessment between Baseline and Week 4
- Patient Global Impression of Change between Week 1 and Week 4
- Pain intensity assessed on an 11-point NRS between Baseline and Week 1, Week 2, and Week 4
- Use of rescue medication between Baseline and Week 1, Week 2, and Week 4

13.1.3 Safety Endpoints

- Adverse events, AEs leading to discontinuation from the study drug, SAEs, and deaths.
- Change from Baseline in clinical laboratory results (including fasting glucose and total lipids [8 to 10 hours after fasting is required for these laboratory testing]), ECG results, body weight, and vital signs.
- Dermal safety: adhesion, irritation, discomfort, and adhesive residue.

13.1.4 Pharmacokinetics Endpoint

Plasma concentrations of diclofenac (for both HP-5000 [REDACTED] and HP-5000 [REDACTED] on Day 14 and 28 (or at the Early Termination Visit).

13.2. Sample Size Determination

Assuming an effect size of [REDACTED] on the change in WOMAC pain score from Baseline to Week 4 between active HP-5000 [REDACTED] and HP-

5000 [REDACTED] treatments and placebo, the probability for detecting the clinically meaningful effect size [REDACTED] or higher will be approximately 67% having 75 evaluable subjects per each active arm and 150 evaluable subjects in the placebo arm. Having 3 treatment arms, the total number of subjects randomized in the study and included in the primary analysis set should be approximately 300. A sufficient number of subjects will be screened to randomize the proposed sample size.

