9.4. Method of Assigning Subjects to Treatment Groups

In this parallel-group randomized study, subjects who will meet study entry criteria will be randomly assigned in a 1:1:2 ratios to receive HP-5000 [REDACTED] HP-5000 [REDACTED] or placebo patches, respectively. The randomization numbers will be assigned sequentially through a

central interactive voice response system (IVRS) as subjects who met eligibility criteria are enrolled into the study. The study center will not be a blocking factor in the randomization schedule. At designated visits, subjects will be given a kit containing sufficient study drug to last until the next scheduled study visit.

The randomization schedule will be prepared by [REDACTED] before the start of the study. No one involved in the clinical conduct will have access to the randomization schedule before official unblinding of treatment assignment. No subject will be randomized into this study more than once.

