13.4. Statistical Analyses

This section presents a summary of the planned statistical analyses. A Statistical Analysis Plan (SAP) that describes the details of the analyses to be conducted will be written prior to database lock. Unless otherwise indicated, all testing of statistical significance will be 2-sided, and a difference resulting in a P value of <0.05 will be considered statistically significant. For analyses involving study site, if the number of subjects per site is small, sites may be pooled for analysis, or omitted from statistical models. The final determination will be made prior to database lock.

Summary statistics will be provided for the variables described below. For continuous variables, these statistical analyses will typically include the number of subjects, mean, standard deviation (SD), median, minimum, and maximum. For categorical variables, these statistics will typically include the number and percentage of subjects in each category.

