SAMPLE SIZE DETERMINATION	Assuming an effect size of 0.32 [REDACTED] on the change in WOMAC pain score from Baseline to Week 4 between active HP-5000 [REDACTED] and HP-5000 [REDACTED] treatments and placebo, the probability for detecting the clinically meaningful effect size [REDACTED] or higher will be approximately 67% having 75 evaluable subjects per each active arm and 150 evaluable subjects in the placebo arm. Having 3 treatment arms, the total number of subjects randomized in the study and included in the primary analysis set should be

	approximately 300. A sufficient number of subjects will be screened to randomize the proposed sample size.
STUDY TREATMENT DURATION	The maximum treatment duration for each subject is 4 weeks. The total duration of study participation for each subject is approximately 9 weeks.

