4.1. Introduction

Data processing, tabulation of descriptive statistics, calculation of inferential statistics, and graphical representations will be performed using SAS® (release 9.4 or higher). If the use of other software is warranted, the final statistical methodology report will detail what software was used for what purposes.

Continuous variable summaries will include the number of subjects or patches (n) with non-missing values, mean, standard deviation (SD), median, minimum, and maximum. Where appropriate, estimates will be presented with 95% confidence intervals (CIs) and standard error (SE).

Categorical variable summaries will include the frequency and percentage of subjects or patches that are in the particular category or each possible value. In general the denominator for the percentage calculation will be based upon the study population for the specified treatment group and overall, unless otherwise specified. The denominator for by-visit displays will be the number of subjects (or patches) in the relevant study population with non-missing data at each visit.

The minimum and maximum will be reported with the same degree of precision (i.e., the same number of decimal places) as the observed data. Measures of location (mean and median) will be reported to 1 degree of precision more than the observed data and measures of spread (SD, SE) will be reported to 2 degrees of precision more than the observed data. Plasma concentration data will be treated as three significant figures for reporting purposes. Percentages will be presented to 1 decimal place, unless otherwise specified.

Unless otherwise indicated, all statistical tests will be conducted at the 0.05 significance level using 2-tailed tests, and p-values will be reported in pvalue6.4 format. Corresponding 95% CIs will be presented for statistical tests.

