5.1.3. Multiple Comparisons/Multiplicity

There will be no adjustments for multiple comparisons for efficacy or safety endpoints.

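### The stated 67% power does not follow from the one effect size visible in the file: if 0.32 still applies, an unadjusted 75 v 150 comparison has about 62%

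*Protocol*

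**What the plan says.** The file binds several versions of the protocol. I take the text that comes first as current, because the SAP cites Amendment 2 and its split of primary and secondary objectives matches that text.

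- **Power and arm sizes.** Protocol 13.2 puts the chance of detecting a clinically important effect, or a larger one, at a level that "will be approximately 67% having 75 evaluable subjects per each active arm and 150 evaluable subjects in the placebo arm". The synopsis and SAP 3.2 repeat this. About 300 subjects are to be randomised and the same number analysed.
- **Effect size.** Section 13.2 reads "Assuming an effect size of [REDACTED] on the change in WOMAC pain score from Baseline to Week 4". A second effect size, the clinically meaningful one, is hidden too. The synopsis of an earlier version in the file shows "Assuming an effect size of 0.32", followed directly by a redaction, and continues in the same sentence: "or higher will be approximately 67% having 75 evaluable subjects per each active arm and 150 evaluable subjects in the placebo arm".
- **Test.** Protocol 13.4 says that "all testing of statistical significance will be 2-sided, and a difference resulting in a P value of <0.05 will be considered statistically significant", and SAP 4.1 agrees. SAP 5.1.3 adds: "There will be no adjustments for multiple comparisons for efficacy or safety endpoints". Each formulation is compared with placebo separately.
- **Allocation.** Protocol 9.4 has subjects "randomly assigned in a 1:1:2 ratios to receive" the two formulations or placebo, so each comparison is 1:2.
- **Model.** The primary analysis is an MMRM with baseline WOMAC pain as a covariate. No power passage gives a correlation or a gain from adjustment.
- **Lower enrolment.** SAP 3.2 adds that power may fall if enrolment is low, but not under 40%. It gives no enrolment figure.

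**The concern.** The earlier synopsis puts an effect size, the arm sizes and a power in one sentence, so the three can be checked against each other without assuming anything about later versions. They do not agree under the planned test. The same power and arm sizes then appear unchanged in the current protocol and the SAP, which makes it likely, though not certain, that the effect size was also carried over.

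The stated power supports the sample size and shapes how a negative result is read. If 0.32 still applies without adjustment, the chance of missing a true effect of that size on a given formulation is about 38% rather than 33%. The sentence also does not say plainly that 67% is the chance of p<0.05, so a reader cannot tell what was computed.

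**Working it through.** **Inputs.** Standardised difference d = 0.32 (earlier synopsis; SD = 1 is my assumption). n = 75 v 150. Two-sided 5%, no multiplicity adjustment. No covariate gain, since none is stated.

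**The plan's figure at d = 0.32**

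- SE of the standardised difference = √(1/75 + 1/150) = 0.1414
- Noncentrality = 0.32 / 0.1414 = 2.263
- Normal approximation: Φ(2.263 − 1.960) = Φ(0.303) = 61.9%
- Noncentral t, 223 df: 61.5%
- If 0.32 was rounded (0.315 to 0.325): 60.2 to 62.9% by t, 60.5 to 63.2% by the normal approximation

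The stated 67% is not reproduced. The gap is about 5 points, and rounding does not close it.

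**Routes at d = 0.32 that also miss 67%**

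| Reading | Power |
|---|---|
| One-sided 5% | 72.9% |
| Both formulations pooled, 150 v 150 | 78.9% |
| At least one comparison significant | 80.5% |
| Both comparisons significant | 43.3% |

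The last two rows use a correlation of 1/3 between the comparisons, from the shared placebo arm: (1/150) / (1/75 + 1/150).

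**Routes that do give about 67%**

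1. *A larger effect.* At 0.34: 0.34 / 0.1414 = 2.404, power 66.8% (t) or 67.2% (normal). Solving for exactly 67% gives 0.339 (normal) or 0.341 (t).
2. *Baseline adjustment.* If 0.32 is scaled by the unadjusted SD of change and baseline correlates with change at r, the effective difference is 0.32 / √(1 − r²). At r = 0.33 this is 0.339, power 66.5% (t). At r = 0.35 it is 0.342, power 67.2% (t).
3. *An equal split of the 225 subjects in one comparison.* SE = √(2/112.5) = 0.1333; 0.32 / 0.1333 = 2.40; Φ(2.40 − 1.96) = 67.0% (66.6% by t). This matches the stated figure but ignores the 1:2 allocation.
4. *67% as the chance that the observed effect reaches some X.* X = 0.32 − 0.440 × 0.1414 = 0.258. The smallest observed difference with p<0.05 is 1.971 × 0.1414 = 0.279, so reaching this X would not by itself be a significant result.

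**Sample size for 67% at 0.32, unadjusted.** About 85 per active arm and 169 or 170 placebo, roughly 340 evaluable in all, against 300 planned.

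**The 40% floor at 0.32.** With 43 per active arm and 86 placebo, SE = √(1/43 + 1/86) = 0.1868; 0.32 / 0.1868 = 1.713; Φ(1.713 − 1.960) = about 40%. The floor is therefore met at about 43 + 43 + 86 = 172 evaluable subjects.

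**The case against.** The strongest reply is that the current inputs cannot be seen. The assumed effect size is blacked out in Protocol 13.2, the current synopsis and SAP 3.2. The value 0.32 comes from one sentence of a superseded version, and the redaction straight after it could hide a range, an SD or a qualifier. The second effect size is hidden everywhere, so 67% may never have been meant as power for p<0.05. The planned model adjusts for baseline, and a modest correlation would bring power to 67%. The gap is also small for a figure given as approximate in a phase 2 trial that is well under 80% power on either number.

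Much of this stands, and it rules out three stronger inferences:

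- A reader might infer that the trial is less sensitive than it claims. The documents do not establish that. An effect of 0.34, or a correlation of about 0.33 to 0.35, would make 67% right.
- A reader might infer that no reading gives 67%. Four do, as shown.
- A reader might infer that the SAP's 40% floor was built on a wrong 67%. The floor has no derivation and no enrolment number, so nothing links the two.

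What does not stand is the use of these possibilities as the plan's explanation. No power passage mentions a correlation or an adjustment. The equal split contradicts the design. An observed-effect reading would leave power for p<0.05 unstated. The mismatch inside the earlier sentence also needs no carry-over between versions.

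**Conclusion.** The point holds conditionally. If the assumed standardised effect size is still 0.32, an unadjusted comparison of 75 v 150 at two-sided 5% has about 62% power (61.5% by t), not 67%. This rests on three assumptions: 0.32 carried over unchanged, it is a standardised difference for each active arm, and no covariate gain was built in. The exact match at an equal split suggests that the 1:2 allocation was overlooked, but it does not prove it.

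The practical weight is modest. The design and analysis are unaffected. The stated power is not delivered by its only visible inputs, and the text does not say what 67% measures.

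**What to change.** In Protocol 13.2, the synopsis and SAP 3.2:

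- State power for p<0.05 per active-versus-placebo comparison, and use that in place of the phrase about detecting a clinically meaningful effect or a higher one.
- Name the inputs used: effect size and its scale, 75 v 150, two-sided 5%, and any baseline correlation with its source.
- If the inputs are 0.32 with no adjustment, restate 67% as about 62%. If an effect of about 0.34 or a covariate gain was used, say so and keep 67%.
- In SAP 3.2, attach an enrolment number to the 40% floor, worked from the confirmed inputs. At 0.32 unadjusted this is about 43 per active arm and 86 placebo.

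The cost is wording in the two documents and possibly a slightly less favourable power figure. No extra subjects are needed, and the analysis does not change.

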8. SUBJECT POPULATION

8.1. Selection of Study Population

The study will enroll up to 300 subjects in a 1:1:2 ratio (HP-5000 [REDACTED] HP-5000 [REDACTED] Placebo) with osteoarthritis pain of the knee. The pain should have been stable over the previous six months prior to Screening (Visit 1).

A screening log of potential study candidates and/or an enrollment log of enrolled subjects must be maintained at each study site.

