8.3. Subject Replacement Criteria

Subjects who withdraw after randomization and the application of the first treatment patch will not be replaced.

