3.1. Overall Design

3.2. Sample Size and Power

Assuming an effect size of [REDACTED] on the change in WOMAC pain score from Baseline to Week 4 between active (HP-5000 [REDACTED] and HP-5000 [REDACTED] treatments and placebo, the probability for detecting the clinically meaningful effect size [REDACTED] or higher will be approximately 67% having 75 evaluable subjects per each active arm and 150 evaluable subjects in the placebo arm. Having 3 treatment arms, the total number of subjects randomized in the study and included in the primary analysis set should be approximately 300. A sufficient number of subjects will be screened to randomize the proposed sample size.

In case of lower subject enrollment, the power to detect clinically meaningful effect of active treatments may drop but not below the threshold of 40%.

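### The stated 67% power makes no allowance for loss between 300 randomised and 300 evaluable, and should be restated at the numbers expected to contribute Week 4 data

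*Protocol*

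**What the plan says.** Protocol 13.2 puts the power at "approximately 67% having 75 evaluable subjects per each active arm and 150 evaluable subjects in the placebo arm", and SAP 3.2 repeats this. Protocol 13.3 equates evaluable with FAS membership: at least one patch applied, a baseline WOMAC pain score and at least one later one. Protocol 13.2 continues that "the total number of subjects randomized in the study and included in the primary analysis set should be approximately 300". Only the number screened is to be adjusted, and only so as to reach the randomised number.

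Protocol 8.1 words the 300 as a ceiling: "The study will enroll up to 300 subjects in a 1:1:2 ratio". SAP 3.3 does the same. Protocol 7.1, 7.3 and 13.2 and SAP section 3 give it as an approximate number. On replacement, Protocol 8.3 says: "Subjects who withdraw after randomization and the application of the first treatment patch will not be replaced".

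Testing follows Protocol 13.4, "all testing of statistical significance will be 2-sided, and a difference resulting in a P value of <0.05", and SAP 5.1.3 adds: "There will be no adjustments for multiple comparisons for efficacy or safety endpoints". Each formulation is therefore compared with placebo at a two-sided 5%.

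The effect size and the clinically meaningful threshold are redacted in the current Protocol 13.2 and in SAP 3.2. The synopsis of an earlier protocol version in the same file, with the same 67% and the same group sizes, reads "Assuming an effect size of 0.32".

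**The concern.** The plan uses one number, 300, both for subjects randomised and for subjects evaluable. These coincide only if nobody is lost in between. Elsewhere the plan expects losses. Protocol 7.1 withdraws subjects who cannot tolerate their dose, and Protocol 8.2.3 provides for withdrawal for adverse events and noncompliance. SAP 5.1.4 discusses missing endpoint values and leaves them unimputed in the primary analysis, and SAP 7.1.1 adds two sensitivity analyses for missing data.

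Counting FAS members also does not measure what the primary comparison needs, which is information at Week 4. A subject who leaves after the Week 1 assessment stays in the FAS but has no Week 4 score. Protocol 13.4.3.1 drops scores taken more than 24 hours after study drug is discontinued. SAP 7.1 goes further: it drops scores taken more than 24 hours after patch removal or detachment, and scores taken within 24 hours of rescue use.

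The figure matters because it is already modest and SAP section 2 looks ahead to a choice for phase III. A non-significant result for either formulation will be judged against 67%. If the true figure is several points lower, that result will look more informative than it is.

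**Working it through.** **Inputs**

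- Two-sided 5% test, each formulation against placebo, unadjusted (Protocol 13.4, SAP 5.1.3).
- 75 evaluable per active arm and 150 on placebo (Protocol 13.2, SAP 3.2).
- Standardised effect d: redacted. It is solved from the stated 67%, and 0.32 from the earlier protocol version is tried separately.
- Loss L: no rate in either document, so 2% to 20% is assumed, in proportion across arms.

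**The plan's own figure.** With the SD set to 1, the standard error is √(1/75 + 1/150) = √0.02 = 0.1414, and power = Φ(d/0.1414 − 1.96).

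- d = 0.32: 0.32/0.1414 = 2.263, and Φ(0.303) = 61.9%. The noncentral t gives 61.5%. This does not reproduce 67%.
- Solving for 67%: d = (1.96 + 0.44) × 0.1414 = 0.339. The noncentral t gives 0.341.

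**Two readings of the 67%.** The plan describes a probability of detecting the clinically meaningful effect or higher. Reading A is the power of the 5% test, so that d is about 0.34. Reading B is the chance that the observed difference reaches a threshold. Reading B gives 67% whenever the true effect exceeds the threshold by 0.44 standard errors, for example true 0.32 and threshold 0.32 − 0.44 × 0.1414 = 0.258.

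**Effect of loss.** Group sizes become n(1 − L), so the standard error is divided by √(1 − L). Reading A is Φ(2.400 × √(1 − L) − 1.96). Reading B is Φ(0.44 × √(1 − L)).

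| Assumed loss L | Subjects left | Reading A | Reading B |
|---|---|---|---|
| 0% | 300 | 67.0% | 67.0% |
| 2% | 294 | 66.1% | 66.8% |
| 5% | 285 | 64.8% | 66.6% |
| 10% | 270 | 62.4% | 66.2% |
| 15% | 255 | 60.0% | 65.7% |
| 20% | 240 | 57.4% | 65.3% |

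Under reading A, one lost subject leaves 66.6% (active arm) or 66.9% (placebo arm). The fall first exceeds 2 points at 14 subjects (14/300 = 4.7%), where power is 64.9%. If d were 0.32, reading A would give about 62% at 300 evaluable, 57% at 10% loss and 53% at 20%.

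**What the table bounds.** It removes whole subjects. A subject who lacks only the Week 4 score still contributes earlier visits to the repeated-measures model. For a given share of missing Week 4 scores spread evenly over the arms, reading A therefore shows the largest fall. Loss concentrated in an active arm costs more per subject.

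**The case against.** The strongest reply is that few subjects will leave the FAS. Baseline WOMAC is an entry criterion, the first post-baseline assessment is at Day 7, and Protocol 10.1.5 requires a WOMAC at the early termination visit. Most treated dropouts will therefore remain evaluable as the plan defines it, and neither document supports a 10% or 20% FAS loss. This stands, and it is why the point concerns Week 4 information more than the FAS count. The size of that loss is also uncertain. Rescue is barred within one calendar day before treatment-phase visits, so the rescue exclusion may affect few scores. The summary table in SAP 7.1.1 also marks rescue as YES for the primary analysis, which sits awkwardly with the exclusion in SAP 7.1.

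SAP 3.2 also tolerates lower power, down to 40%. That sentence concerns lower enrolment, not loss after randomisation. Under reading A with d = 0.339, 40% corresponds to about 152 evaluable subjects, so it does not say what to expect from 300 randomised.

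Four stronger readings are tempting, and the documents do not support them:

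- That the figure fails as soon as one subject is lost. The plan says approximately 67%, and one loss costs 0.1 to 0.4 of a point.
- That 300 is a firm cap. Two sections say so, and several others give an approximate number.
- That nobody can be replaced. Protocol 8.3 covers only withdrawal after the first patch, which is applied the day after randomisation. It is silent on earlier withdrawal.
- That 67% is miscalculated because 0.32 gives 62%. The 0.32 is from a superseded version, the current inputs are redacted, and reading B is compatible with both 0.32 and 67%.

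**Conclusion.** The point holds as a gap in the sample-size statement. The 67% is tied to 300 evaluable subjects, only about 300 are to be randomised, no loss is allowed for, and subjects who withdraw after the first patch are not replaced. The figure therefore describes a trial with essentially no loss.

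The size is modest: under reading A about 2 points at 5% loss, 5 points at 10% and 10 points at 20%. This rests on assumed loss rates, on loss spread evenly over the arms, and on treating missing Week 4 scores as missing subjects, which overstates the fall. Under reading B the fall is under 1 point at 10% loss and under 2 points at 20%. The redactions prevent a choice between the readings, so the sponsor must say which calculation produced 67% and whether 0.32 still applies.

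**What to change.** Keep 300 randomised. In Protocol 13.2 and SAP 3.2:

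1. State the assumed loss rate, the number expected in the FAS and the number expected to contribute a Week 4 WOMAC pain score after the SAP 7.1 exclusions.
2. Give the power per comparison at those numbers, naming the effect size, the test and its level, and whether the figure is the power of that test or the chance of exceeding a threshold. As an illustration only, a 10% loss leaves 300 × 0.90 = 270 subjects and about 62% under reading A.
3. Confirm whether the earlier 0.32 still applies. If it does, explain how it yields 67%.
4. Choose one description of the 300, ceiling or approximate target, and use it in Protocol 7.1, 7.3, 8.1 and 13.2 and in SAP section 3 and 3.3.

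This is a change of text only, with no extra subjects and no change to the analysis. The cost is a slightly less favourable stated power. Recruiting up to 300 evaluable instead would need 300/0.90 = 333.3, so 334 randomised at 10% loss, and the point does not require that.
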